4.2.2 Chronic Toxicity

A 6-month rat study was conducted using oral doses of resveratrol at 300, 1000, and 2,000 mg/kg/day or placebo. Weight loss occurred in the 2,000 mg/kg group. Total bilirubin values were increased in the 1000 mg/kg group with the values returning to normal after the recovery period. The NOAEL was considered to be 300 mg/kg/day.¹² Another 6-month study using oral daily doses of 100, 300, and 500 mg/kg or placebo was conducted in rabbits. No drug-related mortality was observed during the study and there were no apparent drug-related clinical abnormalities. For animals in the 500 mg/kg dose group, modest increases were seen in clinical chemistry parameters of total protein, albumin, GGT, globulin, glucose, urea nitrogen, indirect bilirubin and calcium along with decreases in potassium, but these findings were not present in the recovery animals. The NOAEL was considered to be 500 mg/kg/day.¹²

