9.8 Subject Monitoring

Subjects will be monitored throughout the study by the clinical staff for AEs. In each period, the Investigator or designee will be on site for drug administration and until 2 hours (study Part 1) and until 4 hours (study Part 2) post-dose, and available on call for the remainder of the study. If necessary, the Investigator or designee at the clinical site or a healthcare professional in a nearby hospital will administer treatment for any AE(s). A crash cart or emergency bag containing the necessary rescue material and appropriate medications will be available in the clinic to allow rapid intervention in case of emergency.

Safety parameters, including laboratory results and ECG, will be assessed by the Investigator or designee, using the clinical site's criteria for biomedical laboratory and ECG acceptance ranges as suggested guidelines in making the medical assessment.

Scheduled safety measurements will be repeated according to the clinical site SOPs or upon request from the Investigator or designee. Any abnormal repeated measurement will be evaluated by the Investigator or designee and repeated if judged necessary. Further action may be taken upon the Investigator or designee's request.

Subjects will be advised to notify their health care professional(s) (e.g. physician, dentist, and/or pharmacist) that they are participating in a clinical research study on a drug called resveratrol before taking any medicines or undergoing any medical procedure.

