9.8.6.3 Biochemistry

Biochemistry will be performed at screening and study exit. The following will be assessed: albumin, alkaline phosphatase, AST, ALT, urea, calcium, chloride, glucose, phosphorus, potassium, creatinine, sodium, total bilirubin, and total protein.

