### 9.3 Laboratory Parameters

Biochemistry will be performed at screening and study exit. The following will be assessed: albumin, alkaline phosphatase (ALP), Aspartate Aminotransferase (AST), Alanine Aminotransferase (ALT), urea, calcium, chloride, glucose, phosphorus, potassium, creatinine, sodium, total bilirubin, and total protein.

Serology will be performed at screening. The following will be assessed: HIV antigen and antibody, hepatitis B surface antigen (HBsAg), and hepatitis C virus (HCV) antibody.

Hematology will be performed at screening, at check-in of study Part 2 (Period 4), and at study exit. The following will be assessed: complete blood count with differential, hemoglobin, and hematocrit.

Coagulation tests will be performed at screening. The following will be assessed: prothrombin time/international normalized ratio (PT/INR) and activated partial thromboplastin time (aPTT).

Urinalysis will be performed at screening and at study exit. The following will be assessed: macroscopic examination, pH, specific gravity, protein, glucose, ketones, bilirubin, occult blood, nitrite, urobilinogen, and leukocytes. Unless otherwise specified, microscopic examination will be performed according to internal procedures.

Hematology, biochemistry, urinalysis, urine pregnancy test, vital signs (blood pressure [BP], respiratory rate [RR], heart rate [HR], and oral temperature [OT]), ECG, and AE monitoring will be performed on the last study day. For subjects who are not included in study Part 2, study exit procedures will be completed after the last blood draw of Period 3 (after 32 hours post-dose on Day 2). For subjects who are included in both study parts, study exit procedures will be completed after the last blood draw of Period 4 (after 32 hours post-dose on Day 2). If not possible, all efforts will be made to complete study exit procedures within 14 days after the last participation of the subject in the study.

A urine pregnancy test will be performed at screening and at study exit, and a serum pregnancy test will be performed at check-in of each period.

A urine drug screen (amphetamines, methamphetamines, barbiturates, benzodiazepines, tetrahydrocannabinol, cocaine, opiates, PCP, MDMA, methadone) and a urine cotinine test will

---

be performed at screening. A urine drug screen, a urine cotinine test, and an alcohol breath test will be performed before dosing at check-in of each period.

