Listings of all clinical laboratory results will be provided with the abnormal values flagged with "L" (below normal) and "H" (above normal) for continuous parameters, and "A" (abnormal) for categorical parameters, including the evaluation of the abnormal result as clinically significant or not clinically significant.

Descriptive statistics (mean, median, SD, Min, Max, and sample size) for each clinical laboratory test (continuous variables) will be presented for overall. Change from screening for hematology, biochemistry, and urinalysis will be presented. The unscheduled results will not be included in the summary tables. For categorical variable (urinalysis test), the number of subjects (frequency and percentage) will be tabulated by results (e.g., negative, positive, trace ...). A summary table of shifts from screening to study exit will be provided. Results from repeat tests will not be included in the summary statistics unless the repeat was required (and documented as such) due to technical reasons or an invalid initial result.

For Serology and Coagulation only listing will be provided.

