#### **9.4 Vital Signs**

BP, HR, RR and OT will be measured in a sitting position (except for safety reasons) at screening and study exit.

Descriptive statistics (mean, median, SD, Min, Max, and sample size) will be presented by overall for screening and study exit for each vital sign measurement. Descriptive statistics for change from screening to study exit will be presented. Unscheduled results will not be included in the summary tables. Results from post-dose repeat tests will not be included in the summary statistics unless the repeat was required (and documented as such) due to technical reasons or an invalid initial result.

A listing of all vital signs results will be provided.

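### Unscheduled biochemistry, urinalysis, vital-sign and ECG abnormalities that resolve by study exit enter no summary in their own domain, and 64 of 88 planned dosings have no scheduled value before the next dose

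*SAP*

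**What the plan says.** **Schedule.** Protocol 9.8.6.3 says "Biochemistry will be performed at screening and study exit", and SAP 9.3 says of urinalysis "Urinalysis will be performed at screening and at study exit". Protocol 9.8.1 and 9.8.2, with SAP 9.4 and 9.5, set the same two time points for vital signs and ECG. Hematology differs. Protocol 9.8.6.5 adds check-in samples at Periods 3 and 4, while SAP 9.3 lists only the Period 4 check-in.

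**Unscheduled tests are foreseen.** Protocol 9.8 says "Scheduled safety measurements will be repeated according to the clinical site SOPs or upon request from the Investigator or designee", and SAP section 9 repeats this.

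**Tabulation.** SAP 9.3 says of laboratory results "The unscheduled results will not be included in the summary tables". SAP 9.4 says of vital signs "Unscheduled results will not be included in the summary tables", and SAP 9.5 has the same rule for ECG. Repeat tests also stay out of the summary statistics, "unless the repeat was required (and documented as such) due to technical reasons or an invalid initial result". The one shift table is in SAP 9.3: "A summary table of shifts from screening to study exit will be provided". Laboratory and vital-sign statistics are given overall, not by treatment. Protocol 12.3 likewise frames safety change as screening to exit.

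**Other routes.** All laboratory, vital-sign and ECG results are listed, with flags on abnormal laboratory and ECG values. SAP 9.2 tabulates treatment-emergent adverse events by treatment and overall.

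**The concern.** The study escalates dose within subject, so the natural safety question is what was seen after each dose. In four of the safety domains, the planned tables answer it only for the dose that immediately precedes exit. After any other dose, a result exists only if someone asked for a test, and the SAP then removes that result from the summaries.

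Reversible change is a realistic pattern to guard against. Protocol 4.2.2 reports from a 6-month rat study: "Total bilirubin values were increased in the 1000 mg/kg group with the values returning to normal after the recovery period". Protocol 4.2 describes rabbit bilirubin, urea nitrogen and kidney findings that were gone after recovery. Protocol 4.3.1 lists raised liver and cardiac enzymes and urinary protein in patients. A change after Period 1 or 2 that followed this pattern could be measured, resolve, and then be shown in the shift table as no shift.

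The stopping rules in Protocol 7.5 count clinically significant abnormalities within a dose level and cumulatively. No planned laboratory, vital-sign or ECG table gives such counts by dose level.

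**Working it through.** The plan states no figure on this point, so there is none to reproduce. The check counts dosings and asks which are followed by a scheduled safety value before the next dose.

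**Inputs**
- Part 1: 24 subjects, Periods 1 to 3. Part 2: 16 of them, Period 4 (Protocol 8.1, SAP 3.5).
- Subjects in Part 1 only: 24 − 16 = 8.
- Exit follows the Period 3 32-hour draw for those 8 and the Period 4 32-hour draw for the 16, with up to 14 days' allowance (Protocol 9.9, SAP 9.3).
- Washout: at least 14 days between doses (Protocol 9.2, SAP 3.4).
- Assumption: full completion, no replacements.

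**Planned dosings**
24 + 24 + 24 + 16 = 88, of which 3 × 24 = 72 are in Periods 1 to 3.

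**Dosings followed by a scheduled value before any next dose**

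| Domain | Period 1 | Period 2 | Period 3 | Period 4 | Without a value |
|---|---|---|---|---|---|
| Biochemistry, urinalysis, vital signs, ECG | 0/24 | 0/24 | 8/24 | 16/16 | 88 − 24 = 64 |
| Hematology, protocol schedule | 0/24 | 24/24 | 24/24 | 16/16 | 88 − 64 = 24 |
| Hematology, SAP schedule | 0/24 | 0/24 | 24/24 | 16/16 | 88 − 40 = 48 |

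For the first row, the uncovered dosings are 24 + 24 + 16 = 64. As a share of all dosings, 64/88 = 72.7%. Within Periods 1 to 3, 64/72 = 88.9%.

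**Time to resolve before exit**
From a Period 1 dose there are at least 2 × 14 = 28 days to the Period 3 dose and 3 × 14 = 42 days to the Period 4 dose. From a Period 2 dose the figures are 14 and 28 days.

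**Hematology**
Check-in on Day −1 falls at least 14 − 1 = 13 days after the previous dose. These values are scheduled, so the exclusion rule does not touch them, and SAP 9.3 does not limit hematology change from screening to exit. They do fall outside a screening-to-exit shift table, and a change shorter than about 13 days could still be missed.

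**Tracing one result**
Assume, for illustration only, that 2 subjects have raised bilirubin on an unscheduled test after Period 2 and normal bilirubin at exit. No other subject shifts. The shift table shows 0 of 24. The descriptive statistics use screening and exit values only. Both results are in the flagged listing. They reach the adverse-event tables only if recorded as events; SAP 9.1 states such a rule for physical-examination findings, and the SAP states none for laboratory, ECG or vital-sign values.

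**The case against.** The strongest reply is that little is lost. Every value is listed, laboratory listings carry abnormal flags and a clinical-significance judgement, and 24 subjects can be read case by case. An abnormality that matters would probably be recorded as an adverse event and tabulated by treatment. The SAP follows Protocol 12.3, and keeping unscheduled values out of by-visit means is normal practice. The gap comes from the schedule, and a new table creates no data. The animal and patient signals come from repeated daily dosing, so they do not establish a transient effect of single doses given 14 or more days apart.

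Most of this is fair. The schedule is the main cause, and the toxicology supports plausibility only. By-visit means should stay on scheduled values. What stands against it is that a listing gives no count or denominator by dose, and adverse-event capture depends on a judgement for which the SAP sets no rule in these domains.

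A reader might infer more than the documents support:
- *The abnormality would appear nowhere in the report.* It would be listed, and tabulated if recorded as an adverse event.
- *Only exit values are used in every domain.* Hematology has scheduled check-in values.
- *Nothing after Period 3 is captured.* The 8 subjects in Part 1 only have exit tests after that dose, and withdrawn subjects are tested at or soon after withdrawal.
- *Every unscheduled or repeat result is dropped.* Repeats for technical reasons or an invalid first result are kept.
- *Escalation would be decided without these results.* Protocol 7.5 has both committees review the whole safety data, not these tables.

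**Conclusion.** The point holds for biochemistry, urinalysis, vital signs and ECG. With full completion, 64 of 88 dosings (72.7%) have no scheduled value before the next dose: all 48 in Periods 1 and 2, and the 16 Period 3 dosings of continuing subjects. An unscheduled abnormality in those gaps that resolves by exit enters no laboratory, vital-sign or ECG summary. Early withdrawals would change the count slightly, since their exit tests fall in their own last period.

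For hematology the point is limited to the shift table. The documents give no expected frequency of unscheduled tests or transient abnormalities, so the number of results affected cannot be estimated; 64 of 88 measures where the gap exists, not how often it will matter. This is a reporting weakness worth correcting before the tables are programmed, and it does not affect the PK objectives.

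Separately, the protocol and SAP disagree on the Period 3 check-in hematology sample. The SAP states that it is based on the protocol dated August 20, 2020, and the current protocol cites a document dated November 24, 2020. The two schedules must be reconciled.

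**What to change.** 1. **By-visit statistics.** Keep the descriptive statistics in SAP 9.3, 9.4 and 9.5 on scheduled values, as now.
2. **Laboratory (SAP 9.3).** Add a shift table from screening to the worst value after first dose. Use scheduled, check-in, unscheduled and repeat results, except those documented as technically invalid. Attribute each value to the last treatment received, taking the worst per subject under that treatment. Use as denominator the number of subjects with any post-dose value under that treatment, so untested subjects are not counted as normal.
3. **Vital signs and ECG (SAP 9.4, 9.5).** Add a table of abnormal post-dose values by last treatment received, with the same denominator. Abnormality can be defined by the site's acceptance ranges or, for ECG, by the flags already planned; the SAP should say which, because 9.4 defines no category for vital signs.
4. **Wording.** Amend both the unscheduled-result and the repeat-test sentences in all three sections. Suggested text: *Unscheduled results and repeats not due to a technical reason or invalid first result are left out of the by-visit descriptive statistics only; they are included in the worst-value or abnormal-value table.* Changing one sentence alone would leave the two in conflict.
5. **Hematology schedule.** Reconcile SAP 9.3 and SAP 3.7 with Protocol 9.8.6.5 and 9.11.

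**Cost.** SAP text, one table per domain and abnormality definitions for vital signs; no new data or procedures. The limitation should be footnoted: unscheduled tests are prompted by suspicion, so the tables show the worst values observed among those tested and not incidence by dose. Where nobody ordered a test, they will still show nothing.

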#### **9.4 Vital Signs**

BP, HR, RR and OT will be measured in a sitting position (except for safety reasons) at screening and study exit.

Descriptive statistics (mean, median, SD, Min, Max, and sample size) will be presented by overall for screening and study exit for each vital sign measurement. Descriptive statistics for change from screening to study exit will be presented. Unscheduled results will not be included in the summary tables. Results from post-dose repeat tests will not be included in the summary statistics unless the repeat was required (and documented as such) due to technical reasons or an invalid initial result.

A listing of all vital signs results will be provided.

#### **9.5 Safety ECG**

Supine 12-lead ECG will be performed at screening and study exit.

Descriptive statistics (mean, median, SD, Min, Max, and sample size) will be presented for screening and study exit for ECG. Unscheduled results will not be included in the summary tables. Change from screening descriptive statistics for study exit will also be presented. Results from repeat tests will not be included in the summary statistics unless the repeat was required (and documented as such) due to technical reasons or an invalid initial result.

A listing of all ECG results will be provided with the abnormal values flagged.

## 10. Pharmacokinetic Analyses

### 10.1 Handling of the Below the Lower Limit of Quantification (BLQ) and the No Reportable Concentration

All concentration values that are BLQ occurring prior to dosing as well as samples with no reportable value (NRV) occurring prior to dosing will be replaced by "0.00"; otherwise they (BLQ and NRV) will be set to missing for tabulation, graphical representation and calculation purposes.

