4.3.2 Pharmacokinetics

There are many published human studies dealing with the pharmacokinetics, metabolism, and disposition of resveratrol. Absorption, bioavailability, and metabolism of ¹⁴C-resveratrol after oral and intravenous (IV) doses was investigated in six human volunteers. The absorption of a dietary relevant 25-mg oral dose was at least 70%, but poorly bioavailable ($\leq 1\%$).^{6,16} Peak plasma concentrations of trans-resveratrol were reached at 0.8-1.5 h following oral trans-resveratrol administration at doses 25, 50, 100 or 150 mg, six times/day.¹⁷ A second peak of plasma concentration occurring at 6 hours after the oral dose (but not after the IV dose) may be due to enterohepatic recirculation of conjugated metabolites by reabsorption after intestinal hydrolysis.¹⁶ Absorption is reduced when resveratrol is given with a high fat meal with a delayed time of peak plasma concentrations.¹⁸ There was an increase in systemic exposure to trans-resveratrol with increasing doses of 25-150 mg. Over this dose range, there was a more than dose-proportional increase in AUC_{0-t} and C_{max}. The dose proportionality factor was 2.8 for C_{max} and 6.6 for AUC_{0-t} following a single dose. With repeated doses, steady-state was reached at least by dose 7.¹⁷

Resveratrol has poor water solubility and thus has to be bound to plasma proteins to assure its body distribution and bioavailability. The plasma protein binding of resveratrol in human plasma was 98%.¹⁹

Following oral trans-resveratrol, three metabolic pathways were identified, i.e., sulfate and glucuronic acid conjugation of the phenolic groups and hydrogenation of the aliphatic double bond, the latter likely produced by the intestinal microflora. There was no evidence of enzymatic

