4.4 Rationale for Study Conduct

Absorption of micronized resveratrol is good (~70%) but the compound is almost totally eliminated by first pass metabolism, primarily to glucuronides and sulfates.¹⁰ One of the biggest challenges in translating the therapeutic effects of resveratrol is the poor bioavailability of the drug when it is administered orally. Resveratrol is eliminated from the body extremely quickly and maintaining a therapeutic level in the bloodstream is difficult.^{16,23} In an attempt to improve the oral bioavailability of resveratrol, various formulations and drug delivery systems have been tested but none have been forthcoming, with the exception of multiparticulate formulations, which have shown increased bioavailability.²⁴ Results have shown that high doses of resveratrol are needed to affect disease state; however this causes serious side effects that limit treatment utilization. To bypass the first pass effect, a micellar formulation could allow access to lymphatic distribution. The structure of the product micelle, with a size of appr. 30 nm, is similar to the structure of the naturally formed physiological mixed micelles containing water-insoluble compounds in its core which is enclosed by ambiphilic molecules. The higher bioavailability, which is obtained by the product micellation, is based on the independence of this transport system from the limiting parameters in the formation of the physiological mixed micelle. It is important to appreciate the product micelle's character as an "encapsulation and transport medium". This must not be confused with "nanoparticles" which are often spoken about in nanotechnology. Jupiter Orphan Therapeutics (JOT) is developing a new formulation (called JOTROL) of trans-resveratrol (3,4',5-trihydroxy-trans stilbene) for the treatment of Mucopolysaccharidosis type I (MPS I) and Friedreich ataxia (FRDA). JOTROL is a micellar 10% resveratrol solubilization formulation that is thought to increase the amount of resveratrol and metabolite concentrations in the blood via the lymphatic system.¹⁰

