**5. Primary and Secondary Parameters**

AUC0-inf, AUC0-t and Cmax derived from resveratrol, resveratrol-3-glucuronide, resveratrol-4'-glucuronide, and resveratrol-3-sulfate plasma concentrations will be the primary PK parameters. Other PK parameters derived from plasma concentrations (Residual area, Tmax, T1/2 el, CLsys/F (resveratrol only) and Kel) will be secondary PK parameters (refer to Section 10.3).

For urine PK analyses, Ae0-t, Rmax and TRmax parameters will be calculated using urine concentrations (refer to Section 10.4).

Treatment-emergent AEs (TEAEs) will be tabulated by treatment phase. Safety and tolerability data will be reported using descriptive statistics. (refer to Section 9.2).

---

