### 10.2 Handling of the Difference between the Scheduled and the Actual Sampling Times

The actual clock time for dosing and the actual clock time for each collection time for the PK samples will be recorded using electronic data capture. For all sampling times, the actual sampling times will be calculated as the difference between the sample collection actual clock time and the actual clock time of dosing. The actual post-dose sampling times expressed in hours and rounded off to three decimal digits will be used to calculate the PK parameters, except for pre-dose samples occurring prior to dosing, which will always be reported as zero (0.000), regardless of the time difference. Scheduled sampling times will be presented in concentration tables and mean graphs, while actual sampling times will be presented in the individual graphs in the PK section of the report. A listing of the actual times for PK sampling will be provided for PK samples.

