#### Primary parameter:

AUC0-inf: Area under the concentration-time curve from time zero to infinity (extrapolated), calculated as  $AUC_{0-t} + C_t/K_{el}$ , where  $C_t$  is the last observed measurable concentration.

---

AUC 0-t :	Area under the concentration-time curve from time zero to the last measurable concentration. AUC 0-t will be calculated using the linear trapezoidal-linear interpolation method.
C max :	Maximum observed concentration.

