### 10.5.4 Food-Effect assessment

For evaluation of the food-effect, PK data (ln-transformed  $AUC_{0-t}$ ,  $AUC_{0-inf}$ ,  $C_{max}$  and untransformed  $T_{max}$ ) reported under fed conditions (Period 4) and under fasting conditions (for the same dose level) will be compared using ANOVA from SAS®. The ratio (fed/fasting) and 90% geometric confidence interval will also be calculated for  $AUC_{0-t}$ ,  $AUC_{0-inf}$  and  $C_{max}$ .

If 90% CI for  $AUC_{0-t}$ ,  $AUC_{0-inf}$  and  $C_{max}$  are within 80.00% to 125.00% then no food effect will be concluded.

For all analytes, using GLM procedure in SAS, ANOVA will be performed on ln-transformed  $AUC_{0-t}$ ,  $AUC_{0-inf}$  and  $C_{max}$  at the alpha level of 0.05. The model will include Treatment as fixed effect and Subject as a random effect. Inter- and intra-subject coefficient of variation will be estimated. The ratio of geometric means and 90% confidence interval for the ratio of geometric means, based on least-squares means from the ANOVA of the ln-transformed data, will be calculated for  $AUC_{0-t}$ ,  $AUC_{0-inf}$ , and  $C_{max}$ .

```

SAS® codes for ANOVA: fed vs. fasting
PROC GLM data=basepk;
CLASS TREATMENT SUBJECT;
MODEL VAR = TREATMENT SUBJECT;
RANDOM SUBJECT;
LSMEANS TREATMENT / cl pdiff alpha=0.1;
ESTIMATE 'fed - fasting' TRT 1 -1/cl alpha=0.1;

run;
```

---

Additional statistical analysis may be performed.

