**12. Handling of Missing Data**

For safety,

- If an AE is recorded with an onset date corresponding to a dosing day, but the time is missing, then the AE will be assigned to the treatment phase planned treatment with a dosing planned that day.
- If an AE is recorded with an onset date that does not correspond to a dosing day, but the time is missing, then the AE will be assigned to the treatment phase planned treatment that covers the AE onset day.
- If an AE is recorded with an onset date where day and time are both missing, then the AE allocation to a treatment phase planned treatment will be done on a case by case basis considering available information (e.g. AE onset date, AE end date, AE comments, subject disposition).

For PK, only observed data will be used in the data analysis except for concentration values BLQ as described in Section 10.1. No attempt will be made to extrapolate or interpolate estimates for missing data.

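### SAP 10.1 drops leading BLQ samples from the AUC calculation, which raises AUC0-t and AUC0-inf by 0.5 × tb × C1 compared with setting them to zero; minor, and size not determinable from the documents

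*SAP*

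**What the plan says.** SAP 10.1 gives two rules. BLQ values and samples with no reportable value (NRV) taken before dosing become zero. For all others, "otherwise they (BLQ and NRV) will be set to missing for tabulation, graphical representation and calculation purposes". It does not separate BLQ samples that precede the first quantifiable one (leading), lie between two quantifiable ones (embedded), or follow the last (trailing).

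SAP 10.2 uses actual times for AUC, "except for pre-dose samples occurring prior to dosing, which will always be reported as zero (0.000), regardless of the time difference". A BLQ pre-dose sample is therefore the point (0, 0). SAP 10.3 says that AUC0-t "will be calculated using the linear trapezoidal-linear interpolation method", and defines AUC0-inf as AUC0-t plus the last measurable concentration divided by Kel.

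Nothing elsewhere changes this. SAP 12 says that "only observed data will be used in the data analysis except for concentration values BLQ as described in Section 10.1", which leads back to 10.1. Protocol 12.1.1 refers only to standard non-compartmental methods and has no BLQ rule. Neither document states an LLOQ.

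**The concern.** When absorption starts late, the early BLQ samples show that there was little or no drug in plasma. Setting them to missing discards that information. The trapezoid then fills the gap with a straight rise from time zero, crediting exposure before any drug was measurable.

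The affected parameters matter. SAP 5 states that AUC0-inf, AUC0-t and Cmax from the four analytes' "plasma concentrations will be the primary PK parameters". Under SAP 10.5.4, if the 90% confidence intervals for these three "are within 80.00% to 125.00% then no food effect will be concluded". All three must pass, so one inflated AUC is enough to fail. If the meal delays absorption and fasting does not, the fed AUC carries most of the excess, and a true absence of AUC effect could look like an increase.

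Protocol 4.3.2 gives some reason to expect delay: "Absorption is reduced when resveratrol is given with a high fat meal with a delayed time of peak plasma concentrations".

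**Working it through.** The plan states no figure to reproduce.

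**1. Excess per profile.** Let tb be the last leading BLQ time, t1 the first quantifiable time and C1 its concentration.
- SAP rule: area from 0 to t1 = 0.5 × t1 × C1
- Leading BLQ = 0: area = 0.5 × (t1 − tb) × C1
- Difference = 0.5 × tb × C1

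The Ct/Kel term uses only the terminal phase, so AUC0-inf carries the same excess. On the SAP 10.3 sampling times, the excess is 0.25, 0.50, 0.75 and 1.0 h × C1 when the first quantifiable sample is at 1, 1.5, 2 and 3 h.

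**2. Illustrative profile.** From Protocol Table 1 (1.0 g, unmodified resveratrol): Cmax 117.0 ng/mL, AUCinf 544.8 ng·h/mL. Assumed: one compartment, ka 2 per h, LLOQ 5 ng/mL. Solving for Cmax/AUC = 117.0/544.8 = 0.215 per h gives ke = 0.300 per h. With x = time minus lag, C = 544.8 × ke × ka/(ka − ke) × (e^(−ke·x) − e^(−ka·x)). True AUC0-t is its integral to the last quantifiable sample.

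| Lag (h) | tb (h) | C1 (ng/mL) | Excess (ng·h/mL) | Excess as % of zero-rule AUC0-t | SAP rule vs true | Leading zeros vs true |
|---|---|---|---|---|---|---|
| 0 | none | 37.4 | 0 | 0 | +0.2% | +0.2% |
| 0.25 | 0.25 | 61.8 | 7.7 | 1.5 | +1.3% | −0.2% |
| 0.5 | 0.5 | 94.8 | 23.7 | 4.5 | +3.9% | −0.6% |
| 1 | 1 | 94.8 | 47.4 | 9.2 | +8.2% | −0.9% |
| 1.6 | 1.5 | 84.2 | 63.1 | 12.3 | +11.3% | −0.9% |
| 1.9 | 1.5 | 29.2 | 21.9 | 4.4 | +2.1% | −2.1% |
| 1.95 | 1.5 | 15.4 | 11.6 | 2.3 | −0.8% | −3.1% |
| 2 | 2 | 116.5 | 116.5 | 23.7 | +18.4% | −4.3% |

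The size depends on where the lag falls between samples, not only on its length.

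**3. Average over lag position.** Same model, ka 1, 2 and 4 per h, LLOQ 1 and 5 ng/mL, lags in 0.005 h steps; mean error against true AUC0-t:

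| Lags | SAP rule |
|---|---|
| 0–0.5 h | 0.5–0.9% |
| 0–1 h | 1.5–2.8% |
| 0–3 h | 7–11% |

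With leading zeros the mean error is −0.1% to +0.6% throughout. Over lags of 0–3 h, leading zeros are closer or level at 91–94% of lag positions.

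**4. Exception without a lag.** With assumed AUC 200, LLOQ 20, tb 0.25 h, t1 0.5 h and C1 29.41, the true leading area is 8.80. The SAP rule gives 0.5 × 0.5 × 29.41 = 7.35 and leading zeros give 0.5 × 0.25 × 29.41 = 3.68. Both understate, and the SAP rule is closer.

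**5. Fed/fasting ratio.** With r = 0.5 × tb × C1/AUC(zero rule), the SAP rule multiplies the ratio by (1 + r_fed)/(1 + r_fast). Constructed examples:
- Fed lag 1.1 h, fasting lag 0.1 h: r_fed = 24.607/530.14 = 4.64%, r_fast = 0. The ratio goes from 0.990 (also the true value) to 1.036.
- Equal leading BLQ (tb 0.25 h), larger C1 when fed: 1.0266/1.0044, or +2.2%.
- Longer fed BLQ (0.5 vs 0.25 h), small fed C1: 1.0088/1.0266, or −1.7%.
- Equal BLQ and equal shape: no change.

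What decides the direction is therefore the relative excess, not BLQ duration alone.

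**The case against.** The strongest reply is that the rule is prespecified, the inference is exploratory (Protocol 12.3), and the size is almost wholly assumed. That stands. The only profile available is unmodified resveratrol, whereas "JOTROL is a micellar 10% resveratrol solubilization formulation" (Protocol 4.4). Protocol 4.3.2 reports a later peak with a meal, not a lag. Sampling is dense early on (0.133, 0.25, 0.5 and 1 h), so a short lag costs little. The 7–11% figure depends on lags of up to 3 h that no passage supports. All percentages are for parent drug; nothing was calculated for the three metabolites.

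Three stronger readings are tempting, and the documents support none of them.
- *AUC is always overstated when leading BLQ occurs.* This is exact only against leading zeros. The 1.95 h lag and the no-lag example above go the other way against true AUC.
- *The food-effect result will be biased upward, or only longer fed BLQ can bias it.* The first needs a fed lag that is not established for JOTROL. The second is refuted by the examples in step 5.
- *The rule would hide a meal-induced fall in AUC.* Cmax must also meet the limits and is not touched by the rule. In simulated trials (16 subjects, within-subject CV 20% and fed lags assumed) with a true ratio of 0.80 for both AUC0-t and Cmax, no food effect was concluded in 3–4% under the SAP rule and 2–4% with leading zeros. Masking matters only if Cmax is largely preserved while AUC falls.

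One possible reassurance also fails. A reader might expect a lag to show in the individual curves, but 10.1 removes BLQ from graphs too, so the leading BLQ points are not plotted.

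**Conclusion.** The point holds as a minor one. That AUC0-t and AUC0-inf exceed the leading-zero values by 0.5 × tb × C1 follows directly from SAP 10.1, 10.2 and 10.3, and no other section corrects it. That this is usually an overstatement of true AUC when absorption lags rests on the one-compartment illustration, with the exceptions shown: lags that end just before a sample, and a steep rise with no lag and a high LLOQ.

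The fed/fasting ratio is biased upward if 0.5 × tb × C1/AUC is larger fed than fasting. Whether that will occur with JOTROL cannot be settled from the documents, nor can the size, since they give neither an LLOQ nor a lag. Cmax and Tmax are unaffected. So is the handling of trailing BLQ, because AUC0-t already stops at the last measurable concentration.

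**What to change.** In SAP 10.1, for PK parameter calculation only:
- set BLQ samples before the first quantifiable post-dose sample to zero;
- keep embedded BLQ and all post-dose NRV as missing;
- exclude BLQ after the last quantifiable sample.

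The rule for concentration tables and plots can stay as it is. The change is one sentence and one software setting, best made before concentrations are seen.

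The cost is a small underestimate when true concentrations in those samples lie just under the LLOQ, or when a lag ends just before a sample. The BLQ part is at most LLOQ × (tb + half the gap to t1). With an assumed LLOQ of 5 ng/mL and the first quantifiable sample at 2 h, that is 5 × (1.5 + 0.25) = 8.75 ng·h/mL, or 1.6% of 544.8. Interpolation between samples can add to this in single profiles, as the 1.95 h and 2 h rows show.
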